### 5.2.2 Withdrawal of consent - participant withdraws from all trial participation

Participants are free to withdraw from the trial at any time upon their request or the request of their legally acceptable representative. Withdrawing from the trial will not affect their access to standard treatment or their relationship with the hospital and affiliated health care professionals.

---

For the safety of all participants ceasing trial treatment, reasonable efforts should be made to undertake protocol-specified safety evaluations to capture new safety events and to assess existing, unresolved safety events following withdrawal.

If patients have severe symptoms they will be referred to the most appropriate treating clinician (for example, urology in the setting of kidney stones). Patients will be advised to cease treatment and randomization treatment arm will be made known to patient and clinician.

A dedicated Case Report Form (CRF) page will be used to capture the date of participant withdrawal of consent.

### 5.2.3 Losses to follow-up

A participant will be considered lost to follow-up if they fail to return for two scheduled visits and is unable to be contacted by the trial site staff. The following actions must be taken if a participant fails to return to the clinic for a required trial visit:

- The site will attempt to contact the participant and reschedule the missed visit within one week and counsel the participant on the importance of maintaining the assigned visit schedule and ascertain if the participant wishes to and/or should continue in the trial.
- Before a participant is deemed lost to follow-up, the investigator or designee will make every effort to regain contact with the participant (where possible, 3 telephone calls and, if necessary, a certified letter to the participant's last known mailing address, a letter to the patient's general practitioner and also an email to the patient). These contact attempts will be documented in the participant's medical record or trial file.
- Should the participant continue to be unreachable, he or she will be considered to have withdrawn from the trial with a primary reason of lost to follow-up.

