DESCRIPTION OF SITES ENROLLING PARTICIPANTS	
 
• Peninsula Health (Frankston public hospital)
 
• Frankston Private Hospital
 
• Holmesglen Private Hospital
 
• Cabrini Brighton Private Hospital
 
• Beleura Private Hospital
 

DESCRIPTION OF INTERVENTIONS	
Patients will be allocated to one of two groups:
 
 
• Placebo
 
• Vitamin C 500mg daily
 
 
50 capsules will be given to a patient in a box and patients will be asked to take one capsule daily for fifty days.

TRIAL DURATION	
It is expected the trial will take 12 months to complete.
 
Patients will be enrolled for six months and it is expected the trial will take six months to recruit appropriate numbers.
 
Data analysis is expected to take six months.

PARTICIPANT DURATION	
Participants are enrolled in the study for six months from the date of their index surgery. Patients will be reviewed at four points post-operatively:
 
 
• between 7 and 14 days, combined with post-operative wound check and provision of standard post-operative orthotics/devices
 
• five to six weeks, combined with post-operative x-ray if appropriate
 
• eleven to fourteen weeks
 
• twenty-six weeks following their injury
 

---

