## 3.2 Outcomes

**Table listing objectives and outcomes**

OBJECTIVE	OUTCOME & OUTCOME MEASURE
Primary	
Primary objective – to determine if the proposed protocol is feasible with regards to: 
 
• Recruitment capability
 
• Data collection procedure
 
• Suitability of intervention
 
• Resource availability
 
• Participant response
 
	Recruitment capability: 
 
• Successful recruitment of pre-determined patient numbers
 
 Data collection procedure: 
 
• Successful follow up at established time-points
 
• Qualitative clinical feedback about ease of assessment/data collection
 
• Lost to follow up rate
 
 Suitability of intervention: 
 
• Patient-reported compliance with medication
 
• Patient-reported complication
 
• Qualitative assessment of patient feedback
 
 Resource availability 
 
• Establishing paid and unpaid labour costs required for the trial
 
• Availability of medication and placebo
 
 Participant response: 
 
• Qualitative participant feedback
 
• Participant engagement/follow up
 

Secondary	

 
1. To determine if vitamin C prevents CRPS in patients with lower limb extremity trauma in a dose-response manner
 
2. to determine the incidence of CRPS in lower limb extremity trauma
 
	To determine if vitamin C prevents CRPS in patients with lower limb extremity trauma in a dose-response manner: Patients are evaluated at four points post-operatively: 
 
• 10-14 days
 
• 5-6 weeks
 
• 10-12 weeks
 
• 26 weeks
 
 The outcome of a positive diagnosis for CRPS will be made if the patient meets the 'Budapest criteria' at any of their four post-operative review appointments. This is a combination of asking patients about their symptoms and

OBJECTIVE	OUTCOME & OUTCOME MEASURE

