### 11.3 Methods of analysis

The two secondary aims of this feasibility study will be addressed statistically. For the first secondary aim, diagnosis of CRPS will be ascertained in the form of time-to-event data, and rate ratios will be calculated using univariate Cox proportional hazards regression to directly compare diagnosis rates between the treatment and control groups.

Given the small sample size of this feasibility study, we anticipate randomization may inadequately balance the baseline characteristics of participants in the two treatment groups (e.g. age, trauma vs elective surgery). If necessary, a secondary set of analyses will be performed to adjust for baseline characteristics found to be imbalanced between groups to the extent of a 0.25 standard deviation difference in means (quantitative measures) or an odds ratio of 1.5 (binary measures). These analyses will be conducted using multivariate Cox proportional hazards regression models.

In the survival analyses, loss to follow-up will be considered a censoring event. This equates to an assumption that data is missing at random given the participant's treatment group and the timing of their loss to follow-up. The adequacy of this assumption will be checked in sensitivity analyses that will include both a multiple imputation by chained equations (MICE) approach and adjustment for baseline covariates predictive of propensity for dropout.

A sensitivity analysis will repeat the proportional hazards regression to compare rates of CRPS as diagnosed by the presence of individual Budapest criteria, rather than 3 out of 4 patient-reported symptoms or 2 out of 4 clinician-observed symptoms as required for formal CRPS diagnosis.

For the second secondary aim, the incidence risk of CRPS 6 months post surgery for lower limb extremity trauma patients will be reported as a proportion of the study sample.

Adverse events will be coded as per the Medical Dictionary for Regulatory Activities. Adverse events will be calculated at each visit, and patients may have more than one adverse event. Assessment of severity, frequency and relationship of adverse events to trial intervention will be presented by System Organ Class and information such as start date, stop date, severity, relationship expectedness, outcome and duration will be recorded. Adverse events leading to premature discontinuation from the trial intervention and serious treatment-emergent adverse events will be presented in a table.

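### By its defining sentence, loss to follow-up omits a participant who misses only week 26, so the primary loss rate is understated, and the section's last bullet conflicts with that sentence

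*Protocol*

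**What the plan says.** **Definition.** Protocol section 5.2.3 (listed as 7.5.3 in the contents) has two conditions. The first reads: "A participant will be considered lost to follow-up if they fail to return for two scheduled visits". The second is that site staff cannot reach the person.

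**Procedure in the same section.** The contact steps start after one absence: "The following actions must be taken if a participant fails to return to the clinic for a required trial visit". They end: "Should the participant continue to be unreachable, he or she will be considered to have withdrawn from the trial with a primary reason of lost". The quote is cut there; the reason recorded is loss to follow-up. That last bullet does not repeat the two-visit condition.

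**Visits.** The synopsis, under participant duration, says: "Patients will be reviewed at four points post-operatively". The last is at twenty-six weeks.

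**Use of the loss rate.** The table in section 3.2 lists "Lost to follow up rate" under the data collection part of the primary objective. Attendance at the planned time-points is listed next to it as a separate measure.

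**Analysis.** Section 11.3 says: "In the survival analyses, loss to follow-up will be considered a censoring event". It names no other reason for censoring. The six-month incidence of CRPS "will be reported as a proportion of the study sample". Section 11.2.1 rules out imputation, although section 11.3 plans multiple imputation as a sensitivity analysis.

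**Completion.** Under section 5.2.5 (Trial Closure), completing the trial requires the last visit.

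**The concern.** A rule that needs two missed visits cannot be met by someone whose first missed visit is also the last one planned. That person has not completed the trial under section 5.2.5 and is not lost under the defining sentence of section 5.2.3, so falls in neither class. Week 26 is also the visit at which six-month CRPS status is settled, so the participants left out are ones whose final status is unknown.

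The loss rate is one of the results this trial exists to produce. Section 11.1 gives its purpose as judging feasibility for a later definitive trial and estimating key feasibility parameters. The same term is the only censoring event named for the Cox analysis, so an unclear definition carries over into the comparison of CRPS rates.

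**Working it through.** The protocol states no expected loss rate, so there is no figure to reproduce. The check is a logical one, followed by an illustration with assumed rates.

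**Step 1: definition against visit count.** Take a participant who leaves for good and cannot be reached.

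| First visit missed | Visits missed | Lost under the defining sentence? | Lost if the last bullet governs? |
|---|---|---|---|
| Week 2 | 4 | Yes | Yes |
| Week 6 | 3 | Yes | Yes |
| Week 12 | 2 | Yes | Yes |
| Week 26 | 1 | No | Yes |

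The two readings differ only in the last row. A participant who misses week 26, answers the telephone and still is not assessed is lost under neither reading.

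**Step 2: size, with equal drop-out at each visit.** Assume permanent, unreachable drop-out with probability d at each of the four visits, and set aside participants already diagnosed.

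- Week-26 status missing: 1 − (1 − d)^4
- Counted by the two-visit rule: 1 − (1 − d)^3
- Not counted: the difference, d(1 − d)^3

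| d (assumed) | Week 26 missing | Counted as lost | Not counted (points) | Share of losses not counted |
|---|---|---|---|---|
| 3% | 1 − 0.97^4 = 11.5% | 1 − 0.97^3 = 8.7% | 0.03 × 0.97^3 = 2.7 | 24% |
| 5% | 1 − 0.95^4 = 18.5% | 1 − 0.95^3 = 14.3% | 0.05 × 0.95^3 = 4.3 | 23% |
| 8% | 1 − 0.92^4 = 28.4% | 1 − 0.92^3 = 22.1% | 0.08 × 0.92^3 = 6.2 | 22% |

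With about 100 participants, roughly 3, 4 or 6 people would be left out.

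**Step 3: sensitivity to timing.** Equal drop-out per visit may flatter the rule, because the last interval (weeks 12 to 26) is 14 of the 26 weeks. Assume instead a constant weekly hazard with the same 18.5% missing at week 26. Drop-out before week 12 is then 1 − (1 − 0.185)^(12/26) = 9.0%. The two-visit rule counts 9.0% of participants and leaves out 18.5 − 9.0 = 9.5%, about half of the losses.

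**Step 4: six-month incidence, a separate matter.** Assume 10 observed cases among 100 participants, with m others of unknown week-26 status.

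| m (assumed) | Over the whole sample | Over known status | Upper bound |
|---|---|---|---|
| 10 | 10/100 = 10.0% | 10/90 = 11.1% | (10 + 10)/100 = 20.0% |
| 20 | 10/100 = 10.0% | 10/80 = 12.5% | (10 + 20)/100 = 30.0% |

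None of these figures depends on how loss is defined. A formally lost participant and one who misses only week 26 sit in the whole-sample denominator in the same way.

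**The case against.** **The last bullet already catches these people.** The contact steps start at one missed visit, and the last bullet classes a participant who stays unreachable as withdrawn through loss to follow-up. On that reading, someone who vanishes after week 12 is counted. This stands in part, and it is why one cannot say that such a participant is never counted. It does not settle the matter. The second bullet sets its contact attempts before the point at which loss is declared, which leads back to the two-visit definition. If the last bullet overrides that definition, the section contradicts itself, and the same data could yield 14.3% or 18.5%.

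**Attendance is reported anyway.** A missed week-26 visit will show in the separate attendance measure in section 3.2, and section 5.2.5 makes the person a non-completer. This softens the harm. It does not correct the loss rate, which is an outcome in its own right.

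**The two-visit rule classes people as event-free.** A reader might infer this from sections 5.2.3 and 11.3 together, but the protocol does not say so. For the Cox model, it does not state whether a participant who misses only week 26 is censored at the last visit attended or carried to week 26. For six-month incidence, unknown status does enter as a non-case, but the cause is the whole-sample denominator. It affects formally lost participants equally, and redefining loss would not cure it.

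**The rates are invented.** They are assumptions. Rescheduling within a week and videoconference review may reduce the number with no week-26 assessment. They do not change which participants the definition leaves out.

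**Conclusion.** The point holds in limited form. On the defining sentence of section 5.2.3, a participant who misses only week 26 is not lost to follow-up, and the primary loss rate is understated. On the last bullet, an unreachable participant of this kind may be counted, so the section needs reconciling whichever reading was meant. This is a stated rule, not detail left for an analysis plan.

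Under equal, permanent drop-out of 3% to 8% per visit, the rule leaves out 2.7 to 6.2 percentage points, about 22% to 24% of those without week-26 status. If drop-out is spread evenly over time the share could be about half. These sizes rest wholly on assumed rates and on every drop-out being unreachable.

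The documents do not support the claim that the two-visit rule itself turns unknown outcomes into non-events. The understatement of six-month incidence is a separate consequence of the chosen denominator.

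**What to change.** 1. **Feasibility outcome.** Define loss as no CRPS assessment at week 26 in a participant not already diagnosed. The exception is needed because section 7.4 ends trial follow-up at diagnosis. Report this beside the attendance at each visit that is already planned.
2. **Section 5.2.3.** Keep the two-visit rule only as an operational rule for contact, and reconcile it with the last bullet.
3. **Cox analysis.** Censor every participant without CRPS at the last completed CRPS assessment, whether or not formally lost.
4. **Six-month incidence.** Estimate it by a method that allows for censoring, such as 1 minus the Kaplan-Meier estimate, which relies on a censoring assumption much like the one section 11.3 already makes. Alternatively, report the proportion with the number of known status and the lower and upper bounds.

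The cost is a few sentences and no new data. The downside is a somewhat higher reported loss rate.

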### 5.2.4 Replacements

Participants who sign the informed consent form and are not randomised / assigned trial intervention may be replaced.

Participants who have been randomised / assigned trial intervention may NOT be replaced.

### 5.2.5 Trial Closure

A participant is considered to have completed the trial if he or she has completed all phases of the trial including the last visit or the last scheduled procedure shown in the Schedule of Assessments,

The end of the trial is defined as completion of the last visit in the Schedule of Assessments in the trial at all sites. At this stage, the Sponsor-Investigator will ensure that all HRECs and RGOs as well as all regulatory and funding bodies have been notified.

This trial may be temporarily suspended or prematurely terminated if there is sufficient reasonable cause. If the trial is prematurely terminated or suspended, the Sponsor-Investigator will promptly inform trial participants, HREC and RGO, the funding (where applicable) and regulatory bodies, providing the reason(s) for the termination or suspension. Circumstances that may warrant termination or suspension include, but are not limited to:

- 
- Determination of an unexpected, significant, or unacceptable risk to participants that meets the definition of a Significant Safety Issue (SSI) (for the definition refer to Section 8.1).
  - Insufficient adherence to protocol requirements
  - Data that are not sufficiently complete and/or evaluable
  - Demonstration of efficacy that would warrant stopping
  - Determination that the primary endpoint has been met
  - Determination of futility

In the case of concerns about safety, protocol adherence or data quality, the trial may resume once the concerns have been addressed to the satisfaction of the sponsor, HREC, RGO, funding and/or regulatory bodies.

### 5.2.6 Continuation of therapy

Patients will only be given a 50 day supply of treatment medication. It is expected they will cease this medication before the trial finishes so no continuation of medication will be required.

## 6 SAFETY EVENTS AND RISKS

Please note – the risk of an adverse event with this over-the-counter, commonly used vitamin supplement is very low. In other trials, no adverse events using the medication had been reported, even in doses that are double what we are proposing.

### 6.2 Definitions

#### 6.2.1 Definitions for use in trials involving investigational medicinal products

##### Participant-specific adverse events

Adverse Event (AE): Any untoward medical occurrence in a patient or clinical trial participant administered a medicinal product and does not necessarily have a causal relationship with this treatment.

Adverse Reaction (AR): Any untoward and unintended response to an investigational medicinal product related to any dose administered.

Comment: All adverse events judged by either the reporting investigator or the sponsor as having a reasonable possibility of a causal relationship to an investigational medicinal product would qualify as adverse reactions. The expression ‘reasonable causal relationship’ means to convey, in general, that there is evidence or argument to suggest a causal relationship.

Serious Adverse Event (SAE) / Serious Adverse Reaction (SAR): Any adverse event/adverse reaction that results in death, is life threatening, requires hospitalisation or prolongation of existing hospitalisation, results in persistent or significant disability or incapacity or is a congenital anomaly or birth defect.

Note: Life-threatening refers to an event in which the participant was at risk of death at the time of the event. It does not refer to an event that hypothetically might have caused death if it were more severe.

---

Medical and scientific judgement should be exercised in deciding whether an adverse event/reaction should be classified as serious in other situations. **Important medical events** that are not immediately life-threatening or do not result in death or hospitalisation but may jeopardise the participant or may require intervention to prevent one of the other outcomes listed in this definition should also be considered serious.

Suspected Unexpected Serious Adverse Reaction (SUSAR): An adverse reaction that is both serious and unexpected. A SUSAR will be immediately reported to all stakeholders including the sponsor, investigators, HREC, local governance office and TGA.

### **Safety issues (requiring expedited reporting)**

The following definitions describe additional safety events that require expedited reporting to stakeholders including the Sponsor, Investigators, HREC, local governance office and TGA.

Significant Safety Issue (SSI): A safety issue that could adversely affect the safety of participants or materially impact on the continued ethical acceptability or conduct of the trial.

A SSI is a new safety issue or validated signal considered by the Sponsor in relation to the investigational medicinal product that requires urgent attention of stakeholders. This may be because of the seriousness and potential impact on the benefit-risk balance of the investigational medicinal product, which could prompt regulatory action and/or changes to the overall conduct of the clinical trial, including the monitoring of safety and/or the administration of the investigational medicinal product.

Urgent Safety Measure (USM): A measure required to be taken in order to eliminate an immediate hazard to a participant's health or safety. Note: This is a type of SSI that can be instigated by either the investigator or sponsor and can be implemented before seeking approval from HRECs or institutions.

## **6.2.2 Definitions for use in trials involving investigational medical devices**

### **Participant-specific adverse events**

Adverse Device Effect (ADE): Adverse event related to the use of an investigational medical device

Note: This definition includes adverse events resulting from insufficient or inadequate instruction for use, deployment, implantation, installation or operation, or any malfunction of the investigational medical device. This definition includes any event resulting from use error or from intentional misuse of the investigational medical device.

Adverse Event (AE): Any untoward medical occurrence, unintended disease or injury, or untoward signs (including abnormal laboratory findings) in participants, users or other persons, whether or not related to the investigational medical device.

Note: This definition includes events related to the investigational medical device or the comparator. This definition includes events related to the procedures involved. For users or other persons, this definition is restricted to events related to investigational medical devices.

---

Device Deficiencies: Inadequacy of a medical device with respect to its identity, quality, durability, reliability, safety or performance.

Note: Device deficiencies include malfunctions, use errors, and inadequate labelling.

Serious Adverse Device Effect (SADE): An adverse device effect that has resulted in any of the consequences of a Serious Adverse Event (SAE).

Serious Adverse Event (SAE): An adverse event that:

- a. Led to death
- b. Led to serious deterioration in the health of the participant, that either resulted in
  - a life-threatening illness or injury, or
  - a permanent impairment of a body structure or a body function, or
  - in-patient or prolonged hospitalisation, or
  - medical or surgical intervention to prevent life-threatening illness or injury or permanent impairment to a body structure or a body function
- c. Led to fetal distress, fetal death or a congenital anomaly or birth defect.

Note: Planned hospitalisation for a pre-existing condition, or a procedure require by the Clinical Investigation Plan, without serious deterioration in health, is not considered a serious adverse event.

Unanticipated Serious Adverse Device Effect (USADE): A serious adverse device effect which by its nature, incidence, severity or outcome has not been identified in the current version of the risk analysis report.

Note: An anticipated serious adverse device effect (ASADE) is an effect which by its nature, incidence, severity or outcome has been identified in the current version of the risk analysis report. USADEs require expedited reporting to stakeholders including the Sponsor, Investigators, HREC, local governance office and TGA.

